Summary of eligibility criteria	
Consecutive participants will be assessed for eligibility at the rheumatology outpatient clinic of both participating centers. Patients enrolled in the study must meet all of the following inclusion criteria:
 
 1. Are aged 18 years or older. 2. Have a diagnosis of RA made by a rheumatologist, with a minimal disease duration of 16 weeks or more. 3. Be able and willing to give written informed consent. 4. Are able to understand and write Dutch. 5. Have access to a smartphone with an Android (Requires Android 7.0 or later) or Apple iOS (Requires iOS 13.0 or later) operating system.
Maximum duration of intervention	16 weeks with a window of 2 weeks.
Version and date of final protocol	v6.3 (03-11-2022)
Version and date of protocol amendments	Listed at page 39, 40, 41, 42.

3. Background and rationale

Rheumatoid arthritis (RA) is the most common form of chronic inflammatory arthritis worldwide, with an estimated prevalence of approximately 0.5-1% (1). The condition usually presents with a symmetrically distributed pain, swelling and/or redness of the small joints, such as those of the hands and feet, and significantly impacts patients' quality of life, physical functioning, and work participation (2). In recent years, shifts to a more intensive and targeted treatment paradigm, the so-called treat-to-target (T2T) strategy, along with the development of numerous novel disease-modifying antirheumatic drugs (DMARDs) have considerably improved outcomes for most patients with RA (3). Nevertheless, both international research and recent work from our research group have shown that many patients still report unmet needs despite successful treatment, such as ongoing symptoms of pain and fatigue, or suboptimal psychosocial wellbeing (4-6). Moreover, many patients with RA are confronted with comorbidities that further complicate the management of their disease (7,8).

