4.3 Secondary endpoints

Difference in mean change of total PCS (Pain Catastrophizing Scale) score from baseline to week 16 ± 2w in the intervention group when compared to the control group. The PCS is a patient-reported questionnaire with 13 items scored on a 0-4 Likert scale, resulting in a total score of 0-52 with sub scores for rumination, magnification, and helplessness. Higher scores indicate more catastrophic perceptions concerning pain.

4.3b Exploratory endpoints

- Difference in mean change of total ASES score from baseline to week 16 ± 2w in the intervention arm with weekly RAID questionnaires when compared to the intervention arm with monthly RAID questionnaires.
- Difference in mean change of total PCS score from baseline to week 16 ± 2w in the intervention arm with weekly RAID questionnaires when compared to the intervention arm with monthly RAID questionnaires.
- Difference in mean change of total IPAQ-S score from baseline to week 16 ± 2w in the intervention group when compared to the control group. The IPAQ short form is a 7-item questionnaire enquiring about physical activities during the last 7 days. A specific activity score is obtained for different domains, each being multiplied with the accompanying mean metabolic equivalent (MET) value. This leads to a total score corresponding with low, moderate, or high physical activity.
- Difference in mean change of total PSQI score from baseline to week 16 ± 2w in the intervention group when compared to the control group. The PSQI is a patient-reported questionnaire developed to measure sleep quality through 19 items across 7 domains. The resulting total score ranges from 0-21, with scores of 5 or higher being defined as poor sleep quality.
- To describe participants' continued engagement with the app and to compare it between the weekly and monthly PRO subgroups. Engagement will be defined as:
 - * The proportion of RAID questionnaires with at least one completed item in the Sidekick app, compared to the total number of RAID questionnaires prompted by the app for each participant

during the study period.

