4.4 Trial Design

This will be an investigator-initiated, prospective, open label, parallel group, multi-center, randomized controlled trial (RCT). Participants will be randomized in a 1:1-ratio, using stratified (local) randomization by study center (UZ Leuven or AZ Sint-Lucas Brugge), to either a control group or an intervention group (n = 120 participants in total, 60 in each group). The randomization schedule will be based on center-specific, computer-generated sequences programmed in Research Electronic Data Capture (REDCap), ensuring allocation concealment.

Following randomization, the intervention group will be re-randomized (via computer-generated simple randomization in REDCap) into two arms in a 1:1 ratio (n = 30 participants in each arm).

Participants in intervention arm A will be asked to complete the RAID questionnaire once a week via the Sidekick app, compared to once a month in intervention arm B.

The control group will be followed according to usual care standards. This includes informal screening for psychosocial wellbeing and illness perceptions during outpatient clinic visits, with referral to specific allied health professionals for additional education or non-pharmacological support if needed. The scores derived from questionnaires that form part of the study design can be

[figure not shown]
used as a guide for these discussions. As part of standard care, participants in both the control group and the intervention group will also receive a standardized educational leaflet about RA (attached as additional file), as is already available in the clinic and via the website of patient organization **ReumaNet**.

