- Participant engagement with the app will be analyzed descriptively as 1) the proportion of RAID questionnaires with at least one completed item in the Sidekick app, compared to the total number of RAID questionnaires prompted by the app for each participant during the study period; and 2) several user behavior statistics as described elsewhere. Additionally, participant engagement will be compared between the weekly and monthly RAID groups with unpaired t-tests or Mann-Whitney-U tests depending on data distribution.
- Candidate predictors of a favorable effect of using the Sidekick app on self-efficacy, sleep and physical activity will be studied exploratively with (multiple) linear regression.
- The evolution over time of the RAID scores at baseline, provided in the app (intervention group only) and at week 16 ± 2w, and their association with other outcomes including ASES, IPAQ-S, PSQI and DAS28-CRP/SDAI scores, will be described with linear mixed effects regression models.
- The association of data actively logged in the app (step counts, exercise activities, sleep quality, stress level, and energy level) with (changes in) the validated outcome measures RAID, IPAQ-S, PSQI, ASES, and DAS28-CRP/SDAI collected at baseline and week 16 ± 2w will be reported as Spearman or Pearson correlation coefficients depending on data distribution.

10. Quality assurance

Data collection tools and source document identification:

Source data will be collected and recorded in the study participants' files/medical records. They will be kept on a secured location at all times. The collection and processing of source data (from subjects enrolled in this study) will be limited to those data that are necessary to fulfill the objectives

of the study. These data must be collected and processed with adequate precautions to ensure confidentiality and compliance with applicable data privacy protection laws and regulations. Appropriate technical and organizational measures to protect the data against unauthorized disclosures or access, accidental or unlawful destruction, or accidental loss or alteration must be put in place. Personnel whose responsibilities require access to personal data agree to keep the data confidential.

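### The weekly-versus-monthly comparison of RAID completion will in practice use a rank test that reacts to unequal prompt counts, so it can signal a difference in engagement when per-prompt completion is the same

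*Combined protocol and SAP*

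**What the plan says.** Section 4.3b lists, among the exploratory endpoints, engagement with the app and its comparison between the two reporting frequencies. Its first component is "The proportion of RAID questionnaires with at least one completed item in the Sidekick app", divided by the number of "RAID questionnaires prompted by the app for each participant during the study period". It is therefore one proportion per participant, with that participant's own prompt count as denominator.

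Section 4.4 sets the frequencies: participants in arm A are asked to "complete the RAID questionnaire once a week via the Sidekick app, compared to once a month in intervention arm B". The intervention group is re-randomised "into two arms in a 1:1 ratio (n = 30 participants in each arm"). The synopsis gives the maximum duration of intervention as "16 weeks with a window of 2 weeks".

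Section 9.2 first describes engagement descriptively and then adds the test: "participant engagement will be compared between the weekly and monthly RAID groups with unpaired t-tests or Mann-Whitney-U tests depending on data distribution". The same section applies a 0.05 significance threshold to every analysis. It contains no provision for different denominators: no model for completed out of prompted, no weighting and no matching of prompt weeks. Section 9.1 says the exploratory analyses are not powered.

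**The concern.** Two people who answer each prompt with the same probability have the same expected proportion whether they get 4 prompts or 16, but the proportions are spread differently. Four prompts allow only 0, 25, 50, 75 or 100%, and a perfect score is easy to reach. Sixteen prompts allow 17 values, and a perfect score is much harder. A rank test compares where values fall relative to each other, so it can reject because of the prompting schedule alone.

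At stake is the reading of a named exploratory endpoint. At high completion, a significant result would be reported as better engagement with monthly reporting, and could inform how often patients are asked to report, although behaviour per prompt did not differ.

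**Working it through.** **Inputs from the documents.** Metric and test (9.2); weekly versus monthly prompts and 30 per arm (4.4); 16 ± 2 weeks (synopsis); threshold 0.05 (9.2), taken as two-sided; dropout of at most 10% (9.1).

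**Assumptions.** Prompt counts of about 16 (range 14–18) and about 4 (range 3–5), inferred from frequency and duration. Per-prompt completion p and within-person correlation (ICC), neither of which the documents give. Exactly 30 per arm, although the second randomisation is simple and may not balance exactly.

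**The plan's own figure.** The plan states no error rate or power for this comparison. The arm size can be checked: the Appendix B calculation gives 46.8 per group, 94 in total, and 94 × 1.10 × 1.15 = 118.9, against the planned 120. Then 120 / 2 / 2 = 30 per arm.

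**Step 1: exact check at p = 0.90, ICC 0.**
- Perfect score: 0.9^4 = 0.656 monthly; 0.9^16 = 0.185 weekly.
- Rank quantity P(monthly > weekly) + ½ P(tie):
  - monthly at 100%: 0.656 × (0.815 + 0.185/2) = 0.595
  - monthly at 75%: 0.292 × (0.017 + 0.051/2) = 0.012
  - lower values contribute almost nothing.
- The sum is 0.608, where no difference would be 0.5. Both means are 0.90.

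**Step 2: which test the rule selects.** Section 9.2 names no normality criterion. With Shapiro-Wilk in either arm as a stand-in, essentially 100% of simulated datasets went to Mann-Whitney, so the two-stage error equals the Mann-Whitney error.

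**Step 3: simulated error at nominal 5%.** 10,000 runs per cell, 30 versus 30, 16 versus 4 prompts, no attrition. Each person's completion probability is drawn from the same beta distribution in both arms (constant at ICC 0).

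| Completion p | Mann-Whitney, ICC 0–0.5 |
|---|---|
| 0.50 | 5.1–6.1% |
| 0.70 | 7.0–7.8% |
| 0.80 | 8.7–13.0% |
| 0.90 | 10.4–35.1% |

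Welch on the same proportions rejects in about 3–6% over the range of scenarios tried. Repeat runs move cells by about a percentage point, hence the rounded ranges 5–6, 7–9, 9–13 and 10–36%. At p = 0.90, error falls steadily as ICC rises: about 36% at 0, 28% at 0.1, 22% at 0.2, 16% at 0.3 and 10% at 0.5. At ICC 0.7 it is about 5–7% for the completion levels tried. At p = 0.90 or above, 94–100% of false positives favour the monthly arm. The problem is symmetric: at 10% completion the rates are similar but favour the weekly arm.

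**Step 4: sensitivity at p = 0.90, ICC 0–0.5.** 27 per arm: 10–33%. 14 versus 3 prompts: 13–55%. 18 versus 5 prompts: 9–22%.

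**Step 5: does a test of means suffice?** Let participants in both arms stop using the app at the same weekly rate, with 90% completion while active, and place monthly prompts at weeks 4/8/12/16 or 1/5/9/13. The arm means now differ because the prompts fall at different times. Welch error is about 8–9% at 5% weekly stopping and about 12–15% at 10%. Restricting the weekly arm to the weeks when the monthly arm is prompted brings it back to about 4–6% in every case tried.

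**Step 6: precision cost of matching.** The variance of one person's proportion over m prompts is p(1−p)[ICC + (1−ICC)/m]. At p = 0.90 without attrition, the standard error of the difference is:
- ICC 0, all prompts: √[0.09 × (1/16 + 1/4)/30] = 0.031; matched: √[0.09 × (1/4 + 1/4)/30] = 0.039.
- ICC 0.2, all prompts: √[0.09 × (0.25 + 0.40)/30] = 0.044; matched: √[0.09 × (0.40 + 0.40)/30] = 0.049.

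**The case against.** **The comparison is exploratory.** This stands. A reader might infer that the main feasibility contrast of the trial is compromised. The documents do not support that: the feasibility objective in 4.1 concerns engagement overall and names no weekly-monthly contrast, 9.2 treats engagement as descriptive first, and both 9.1 and 9.2 give the arm comparisons exploratory status.

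**The plan does not prescribe Mann-Whitney.** Also true. It allows a t-test, and that branch holds about 5% error without attrition. That the rule ends at Mann-Whitney is an inference, though a safe one for a five-valued proportion.

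**The large figures need favourable inputs.** Largely true. About 36% requires 90% completion and no variation between people. Section 3 reports wide variation in compliance, and 4.1 allows no incentives beyond built-in messages. Against that, one answered item counts as completion, RAID is the only app function actively stimulated (6.1), and people who never use the app are excluded from analyses (5.2). High completion is therefore possible but not established.

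**Calling it a false positive presumes a per-prompt question.** Partly true. The two distributions of proportions do differ. The error lies in reading a rejection as a difference in engagement, which is how this endpoint would naturally be read.

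**Conclusion.** The point holds for the RAID proportion. The distribution-dependent rule will almost always lead to Mann-Whitney, and that test then responds to about 16 versus about 4 prompts. The excess error is negligible near 50% completion or with very strong within-person correlation, modest at 70–80%, and material near 90% when that correlation is low to moderate. These sizes rest on inferred prompt counts, assumed completion and correlation, 30 per arm and no attrition.

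The severity is minor to moderate. A reader might take about 36% as the expected error in this trial; it is the top of an assumed range. A reader might also conclude that switching to Welch settles the matter; it does not if app use declines. Log-ins and other user statistics have no prompt denominator and are not affected, nor are the primary and secondary conclusions.

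**What to change.** In 9.2, for the RAID proportion only, replace the choice by distribution with the difference in mean completion proportion and a Welch 95% CI. A quasi-binomial or GEE logistic model of completed out of prompted, with participant-clustered standard errors, is an acceptable alternative (error about 3–8% in the same no-attrition scenarios).

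State the weeks in which the monthly arm is prompted, and compare the arms on those weeks, using only the weekly arm's prompts that fall in them. The weekly arm's full completion can still be described.

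The cost is a short change to the text and no new data. The matched comparison discards some weekly-arm prompts and loses a little precision: without attrition at 90% completion, the standard error rises from 3.1 to 3.9 percentage points at ICC 0, and from 4.4 to 4.9 at ICC 0.2.

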6	V3.1	26-11-2021	[name]	Advice considering changing sample size, data handling and study flowchart.
7	V3.2	11-12-2021	[name]	Adaptation trial flowchart with deletion of the unscheduled visit, correction of trial periods, adaptation lay- out.
8	V4.0	17-01-2022	[name], [name], [name]	Correcting time intervals, correcting sample size, correcting small errors, adding part about data handling, refining lay-out.
9	V4.1	23-01-2022	[name], [name], [name].	Extending trial to 32 weeks with cross-over design considering the control group, adding third visit

				moment, updating list of abbreviations, adapting sample size, making new study diagram, concordance between study synopsis and the whole document.
10	V5.0	20-02-2022	[name], [name]	The third evaluation moment at week 32 was dropped, the study will again end at week 16 as stated before. The intervention group will be cut in half with one group getting the RAID questionnaire weekly, the other one monthly, sample size was adjusted for this. The FFQ was dropped as it could not provide a quantitative result and was deemed too extensive to complete.
11	V6.0	24-02-2022	[name]	Extensive formatting,

				including changes to the title. Adaptation of secondary and exploratory endpoints, including adaptation of the sample size calculations and consequent changes in the randomization procedure.
12	V6.1	12-03-2022	[name], [name], [name]	Correcting minor incompatibilities, considering CDAI and SDAI for measuring disease activity, change of the protocol acronym to AEGORA: App-based Education and Goal-setting in Rheumatoid Arthritis.
13	V6.2	08-09-2022	[name]	Fine-tuning minor incompatibilities.
14	V6.3	03-11-2022	[name], [name], [name]	Addressing comments of Ethical Committee

Appendix A. Short overview of educational content in Sidekick app

Appendix B. R script for sample size calculations

```
library(pwr)
library(epiR)

#---- Primary outcome: ASES
d <- 5.5/9.4
power <- pwr.t.test(d = d, sig.level = 0.05, power = 0.80, type = "two.sample", alternative =
"two.sided")
samplesize <- round(power$n * 2)

# Accounting for 10% drop-out
samplesize <- samplesize*1.10

# Accounting for possible need for non-parametric tests
samplesize <- round(samplesize*1.15)

#---- Secondary outcome: PCS (non-inferiority)
power <- epi.ssninf(treat = 20.3, control = 20.3, sd = 12.3, delta = 7.7, n = NA, r = 1,
power = 0.80, alpha = 0.025)

# Accounting for 10% drop-out
samplesize <- power$n.total*1.10

# Calculation of power with 120 participants and 10% drop-out (= 108):
power <- epi.ssninf(treat = 20.3, control = 20.3, sd = 12.3, delta = 7.7, n = 108, r = 1,
power = NA, alpha = 0.025)
```
